## B. STUDY DESIGN AND OVERVIEW OF ANALYSIS PLAN

A retrospective cohort study design is proposed to examine TRALI occurrence among HCA patients transfused in a hospital inpatient setting between September 2013 and September 2015. Within this cohort, capture of potential TRALI cases, risk factors for TRALI, and relevant transfusion exposures in HCA’s Sentinel database will be described, and incidence rates of TRALI subsequent to plasma, platelet, packed red blood cell administration using HCA’s Sentinel database will be calculated. Medical chart reviews will be conducted to confirm the outcome (TRALI) and the transfusion exposure, and the positive predictive values of each electronic algorithm will be evaluated. The gold standard will be medical chart confirmed outcomes and transfusion exposures.

Unadjusted TRALI rates (per 100,000 inpatient transfusion stays) will be calculated overall, by year, blood component groups, sex, age, race, and number of units transfused. If appropriate transfused unit data are available, unadjusted TRALI rates per number of units transfused will also be calculated. Medical charts will be utilized to confirm the TRALI outcome and transfusion exposure in identified TRALI cases, and the positive predictive value of an ICD-9-CM based algorithm for identifying TRALI will be presented. Similarly, the positive predictive value of reported transfused product exposure and medical chart confirmed exposure in identified TRALI cases will be presented.

As HCA is a new Sentinel Data Partner, exploratory analyses are included as feasibility analyses (see page 2). The workgroup will explore the potential to compare blood component specific TRALI rates, examine TRALI patient and transfusion risk factors, and ability to identify specific categories of blood components, including component type and processing method (e.g., leukocyte-reduced, irradiated). Finally, the workgroup will describe which HCA data elements are included in the SCDM that are useful/relevant for studying TRALI, and which inpatient data elements could be useful but have not been included, and to assess the feasibility and need for adding these elements based on their availability, accuracy, and usefulness for blood and other biological products.

The plan is shown schematically below:

Relative Timing	Method	Analysis	Data to use
Initial	Descriptive analysis examining capture of potential TRALI cases, risk factors for TRALI, and relevant transfusion exposures	Primary	Transfusions: HCA Sentinel Data Outcome: HCA Sentinel Data
	Descriptive analyses, examining potential to compare blood component specific TRALI unadjusted rates	Exploratory	Transfusions: HCA Sentinel Data Outcome: HCA Sentinel Data
	Descriptive analyses, examining: 
 
ability to identify specific categories of blood components, including component type and processing method (e.g., leukocyte-reduced, irradiated)
 
methods for reducing any relevant missing transfusion information in HCA’s Sentinel database
 
distribution of possible patient risk
 
	Exploratory	Transfusions: HCA Sentinel Data Outcome: HCA Sentinel Data

Relative Timing	Method	Analysis	Data to use
	
factors, such as age, sex, and relevant comorbidities, among cases of TRALI
 
 
distribution of possible transfusion risk factors, such as volume of transfusion, indication, pregnancy history, component processing (e.g., leukoreduction, irradiation) among cases of TRALI
 
transfusion stays with TRALI vs without TRALI, comparing demographic characteristics (age, gender, race), length of stay, mechanical ventilation (identified with ICD-9-CM procedure codes) and inpatient mortality
 
		
Final	Descriptive analysis, calculating unadjusted rates of TRALI in identified cohort	Primary	Transfusions: HCA Sentinel Data Outcome: HCA Sentinel Data
	Validation of TRALI outcome, in identified TRALI cases	Primary	Transfusions: HCA Sentinel Data Outcome: HCA Sentinel Data and Chart Review
	Validation of transfusion exposure in identified TRALI cases	Primary	Transfusions: HCA Sentinel Data Outcome: HCA Sentinel Data and Chart Review
	Descriptive analysis identifying which HCA data elements are included in the SCDM that are useful/relevant for studying TRALI, and which inpatient data elements could be useful but have not been included, and to assess the feasibility and need for adding these elements based on their availability, accuracy, and usefulness for blood and other biological products	Exploratory	Transfusions: HCA Sentinel Data Outcome: HCA Sentinel Data

### C. EXPOSURES OF INTEREST

Primary objectives of this protocol require the electronic identification of blood component type (i.e., plasma, platelets, and packed red blood cells) in HCA’s Sentinel database. HCA currently utilizes two coding systems to identify transfusions, ISBT 128 and Codabar. These code systems allow for identification of blood component type, and may in theory also allow for identification of processing method (e.g., leukocyte-reduced, irradiated) at HCA. ISBT and Codabar, include > 4,500 codes and > 1,500 codes, respectively. At HCA, historically there has been use of both code types to identify transfusions. Although both systems are still in use at HCA, there has been an increased uptake in use of ISBT codes and a decrease in use of Codabar codes over time. For example, by mid-2015 less than 1% of HCA transfusions were coded with a Codabar code.

Databases of ISBT codes are updated monthly by the International Council for Commonality in Blood Banking Automation, Inc. (ICCBBA), but Codabar codes are no longer updated. Endorsed by the AABB (Advancing Transfusion and Cellular Therapies Worldwide), ICCBBA is an international non-governmental organization (NGO) in official relations with the World Health Organization (WHO) that manages, develops, and licenses ISBT 128, the international information standard for the terminology, coding and labeling of medical products of human origin.

The National Healthcare Safety Network’s (NHSN) variable of Prod\_CDC will be used in combination with ISBT and Codabar code systems to collapse these lengthy code lists into relevant blood component categories. Categories included in the NHSN system are listed in **Table 3**. Essentially, each ISBT or Codabar code will receive a NHSN label to allow for collapsing of granular codes into relevant categories. The latest version of the NHSN’s data dictionary and the ICCBBA’s databases available at the time of program development will be used to accomplish this task.

Exploratory objectives included in this protocol require the electronic identification of component processing (e.g., leukoreduction, irradiation) within HCA’s Sentinel database. Although highly specific codes exist with the ISBT and Codabar systems which could in theory be used to identify component processing, a thorough exploration of HCA data must occur. There may be missing ISBT or Codabar codes, or codes which are not known to be valid. Thus, there will be an attempt to characterize any relevant missing transfusion information. This characterization may require working with HCA staff to interpret the product information included in the Sentinel Inpatient Transfusion Table (**Table 7**), or other available information. It is possible that local coding across HCA’s network may dictate how relevant blood products/components are coded in HCA data, and thus the usefulness of specific codes for identification of blood component processing is unknown. To accomplish exploratory objectives, the same coding systems described above will be used, and the workgroup will work closely with HCA to learn more about coding practices and opportunities to identify component processing within HCA data broadly.

Additional exposure related variables to be explored in this protocol include transfusion risk factors for TRALI, such as ability to identify transfusion timing, transfusion environment (i.e., ICU, Floor, Operating room), number of transfusions per hospitalization and volume transfused. The feasibility of identifying these variables in the HCA Sentinel database will be explored, and if possible, frequency distribution among TRALI cases will be characterized.

**Table 3: Method for categorizing blood products/components the National Healthcare Safety Network (NHSN): Variable Prod\_CDC**

Broad Categorization	Description
Plasma	APHPLASMA - Apheresis plasma
	WBDPLASMA - Whole blood derived plasma
Platelets	APHPLAT - Apheresis platelets
	IRAPHPLAT - Irradiated apheresis platelets
	IRRAPHPLAT - Irradiated leukocyte reduced apheresis platelets
	IRLRWBDPLAT - Irradiated leukocyte reduced whole blood derived platelets
	IRWBDPLAT - Irradiated whole blood derived platelets
	LRSPHPLAT - Leukocyte reduced apheresis platelets
	LRWBDPLAT - Leukocyte reduced whole blood derived platelets

Broad Categorization	Description
	WBDPLAT - Whole blood derived platelets
Red Blood Cells	APHRBC - Apheresis red blood cells
	IRAPHRBC - Irradiated apheresis red blood cells
	IRLRAPHRBC - Irradiated leukocyte reduced apheresis red blood cells
	IRLRWBDRBC - Irradiated leukocyte reduced whole blood derived RBC
	IRWBDRBC - Irradiated whole blood derived red blood cells
	LRAPHRBC - Leukocyte reduced apheresis red blood cells
	LRWBDRBC - Leukocyte reduced whole blood derived red blood cells
	WBDRBC - Whole blood derived red blood cells
Whole Blood	WB - Whole blood
Other	CRYO – Cryoprecipitate
	GRAN – Granulocytes
	LEUK – Leukocytes
	LYMPH – Lymphocytes
	MNC - Mononuclear cells
	SERUM – Serum

#### D. OUTCOME DEFINITION

Potential cases of TRALI will be identified with the codes included in **Table 4**. As TRALI is likely under-diagnosed, this protocol focuses not only on the TRALI specific ICD-9-CM code (ICD-9 518.7), but also on specific respiratory failure codes described above in combination with an ICD-9-CM code for a transfusion reaction. **Table 5** includes the electronic criteria to identify potential cases of TRALI in the HCA Sentinel database. These criteria include ICD-9-CM codes, as the time-period of interest for this protocol precedes the transition to ICD-10-CM coding in the United States.

**Table 4: Working list of codes for TRALI and transfused ALI**

ICD-9-CM Code	Definition
518.7	Transfusion-related acute lung injury
518.81	Acute respiratory failure
518.82	Other pulmonary insufficiency, not elsewhere classified code in any position
999.80	Other infusion and transfusion reaction
999.89	Other transfusion reaction
E934.7	Natural blood and blood products causing adverse effects in therapeutic use

**Table 5: Electronic criteria to identify potential cases of TRALI**

Criteria	ICD-9-CM Code(s)
Criterion A	TRALI, ICD-9-CM code in any position (518.7)
Criterion B	Acute respiratory failure ICD-9-CM code in any position (518.81), WITH code for a blood transfusion reaction (999.80 or 999.89 or E934.7)
Criterion C	Other pulmonary insufficiency (518.82), WITH code for a blood transfusion reaction (999.80 or 999.89 or E934.7)
Any TRALI Criteria	Criteria A, and/or B, and/or C listed above

The above criteria and codes will be used to identify TRALI cases in HCA’s Sentinel database and will be used to calculate incident rates of TRALI subsequent to plasma, platelet and packed red blood cell administration based on the electronic criteria. Stratifications will be made by TRALI criterion as feasible. These TRALI criteria will also be used to identify TRALI cases in HCA’s Sentinel database for chart review.

Medical charts will be obtained for relevant cases, reviewed and adjudicated by clinical experts.

This chart information will identify chart validated cases, which will be the gold standard for the primary validation objective. Please see section E.

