#### C. INPATIENT RED BLOOD CELL, PLASMA AND PLATELET ADMINISTRATION

More than 90% of blood transfusions in the United States are performed in inpatient settings. The 2013 National Blood Collection and Utilization Survey includes estimates for the amount of blood collected and transfused in the United States per year. This report estimates 13,180,000 whole blood (WB) and red blood cell (RBC) units were transfused in the United States in 2013. Estimates of platelets transfused totaled 2,281,000 units (including 128,000 whole blood derived platelets and 2,137,000 apheresis

platelets). An estimated 3,624,000 units of plasma were also transfused. Thus, in 2013 the most commonly transfused blood component pertaining to this protocol was RBCs, followed by plasma, and platelets. These numbers provide some context in terms of what may be expected in terms of blood components transfused per year in HCA hospitals.

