**Table 1: Transfusion Related Acute Lung Injury (TRALI) definitions**

Definition	Clinical Description
Definitive TRALI 	
 
1. No evidence of acute lung injury (ALI) prior to transfusion AND
 
2. ALI onset during or within 6 hours of transfusion AND
 
3. Hypoxemia defined by any of these methods: 
 
•PaO2 / FiO2 ≤300 mm Hg
 
•Oxygen saturation is < 90% on room air
 
•Other clinical evidence
 
 AND
 
4. Radiographic evidence of bilateral infiltrates AND
 
5. No evidence of left atrial hypertension (i.e. circulatory overload) AND
 
6. No temporal relationship to an alternative risk factor for ALI during or within 6 hours of completion of transfusion
 

Possible TRALI 	Same as above EXCEPT there is a temporal relationship to a specific ALI risk factor (Table 2)
Delayed TRALI definition, defined in critically ill patients	
Delayed TRALI 	Same as for possible TRALI except allows for symptom onset within 6 to 72 hours of blood transfusion

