## 2. Calculation of Incidence Rates

Unadjusted incidence rates of TRALI occurrence after any transfusion will be calculated, along with 95% confidence intervals. Any transfusion will be defined as exposure to plasma, platelets (PLT), or packed red blood cells (RBC) as defined in HCA's Sentinel database. TRALI will be defined using ICD-9-CM based codes in HCA's Sentinel database, and the primary analysis will focus on TRALI as defined by criterion A (Table 5). Unadjusted TRALI rates (per 100,000 inpatient transfusion stays) will be stratified by year, blood component groups (i.e., plasma, PLT, and RBC), age, sex, race, and quantified units. If data on the number and type of component unit(s) transfused are available, unadjusted TRALI rates per number of units transfused will also be calculated. If feasible, quantified units will be examined separately for children and adults.

In addition to identifying rates of TRALI occurrence after any exposure to plasma, PLT, or RBC during an inpatient stay, if adequate sample size is available we will also explore exposure to RBC-only, plasma-only, and PLT-only. Exposure to multiple blood component types (i.e., plasma and PLT, RBC and PLT, plasma and RBC, plasma and RBC and PLT) or non-specific blood components (if relevant) will also be described.

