**Table 7: Inpatient Transfusion, HCA Table structure as of May 2016**

Variable Name	Variable Type and Length (Bytes)*	Values	Definition / Comments / Guideline
PatID	Character(Site specific length)	Unique member identifier	Arbitrary person-level identifier. Used to link across tables. Derivative of HCA Patient Account Number.
EncounterID	Character(Site specific length)	Unique encounter identifier	A unique combination of PatID, ADate, Provider and EncType. Used to link the Encounter, Diagnosis, Procedure, Inpatient Pharmacy, and Inpatient Transfusion tables.
TransID	Character(15)	Unique transfusion administration identifier	For mapping back to source data
TransCode	Character(15)	Code value for an infusion product	Must be paired with the correct TransCode_Type
TransCode_Type	Character(2)	Code type for the value in TransCode	Transfusion product code type. This variable combined with the TransCode variable should be used to capture any type of Inpatient Infusion product in the source data. Other code types will be added as new terminologies are used. IS=ISBT CD=CODABAR
Orig_TransProd	Character(Site specific length)	Original product name/mnemonic	Name of product within Data Partner
BloodType	Character(3)	Blood type: A, B, O, AB (upper case) with RH factor (+, -, or null only)	Blood type and Rh factors, left-justified. Convert any text Rh factor to symbols (e.g., "pos" to "+", "negative" to "-"). Rh factor can be blank.
TDate_Start	Numeric(4)	SAS date value	Administration start date
TTime_Start	Numeric(4)	SAS time value HH:MM	Administration start time
TDate_End	Numeric(4)	SAS date value	Administration end date
TTime_End	Numeric(4)	SAS time value HH:MM	Administration end time
EncType	Character(2)	ED = Emergency Department	ED encounters only
		IP = Inpatient Hospital Stay	Includes all inpatient stays, same-day hospital discharges, hospital transfers, and acute hospital care where the discharge is after the admission date. This also includes ED visits that become inpatient stays.
		IS = Non-Acute Institutional Stay	Includes hospice, skilled nursing facility (SNF), rehab center, nursing home, residential, overnight non-hospital dialysis and other non-hospital stays.
		OA = Other Ambulatory Visit	Includes other non overnight AV encounters such as hospice visits, home health visits, skilled nursing facility visits, other non-hospital visits, as well as telemedicine, telephone and email consultations.

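### The primary TRALI rate is described as following transfusion, but its Criterion A numerator does not require the diagnosis to come after a transfusion in that stay

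*Protocol*

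**What the plan says.** Section IV.D, Table 5, defines Criterion A as "TRALI, ICD-9-CM code in any position (518.7". Criterion B is "Acute respiratory failure ICD-9-CM code in any position (518.81), WITH code for a blood transfusion reaction (999.80 or 999.89 or E934.7". Criterion C pairs 518.82 with the same reaction codes. Table 5 gives no position for 518.82, but Table 4 describes it as "Other pulmonary insufficiency, not elsewhere classified code in any position".

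The text under Table 5 says that these criteria "will be used to calculate incident rates of TRALI subsequent to plasma, platelet and packed red blood cell administration based on the electronic criteria". Section IV.F.2 then states: "Unadjusted incidence rates of TRALI occurrence after any transfusion will be calculated, along with 95% confidence intervals". It makes Criterion A the primary analysis, expresses rates per 100,000 inpatient transfusion stays, and stratifies them by component group and number of units, among other factors.

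The schematic table in section IV.B gives HCA Sentinel data as the only outcome source for the rates. Chart review is listed only for the two validation rows.

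The clinical definition used by the adjudicators (section III.D, Table 1) begins with "No evidence of acute lung injury (ALI) prior to transfusion" and requires onset during transfusion or within 6 hours of it.

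**The concern.** The rate is presented as an incidence after exposure, so the exposure has to come first. The electronic numerator needs only two facts about a stay: a 518.7 code somewhere in the list, and a relevant transfusion at some point. A stay that begins with TRALI and includes a transfusion on a later day meets both.

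Two results are at stake. The overall Criterion A rate would include events that began before any transfusion recorded in the stay. The component-specific rates could assign a case to the component given afterwards: a patient admitted with TRALI after platelets elsewhere and then given red cells would count as a red-cell case. That bears on the second primary objective and on the first exploratory objective, which looks at comparing components.

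**Working it through.** **Is order imposed anywhere in the electronic rate?**

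- Table 5: codes only, with no timing condition.
- IV.F.2: counts any exposure to plasma, platelets or red cells during the stay, with no interval or sequence.
- IV.B schematic: electronic outcome data only for the rate.
- IV.E: charts are drawn whatever the transfusion status or timing. This suits validation, and it shows that out-of-order cases were foreseen.
- IV.E and IV.F.3: adjudication applies the order in Table 1, but its stated output is the PPV. No section feeds it back into the rate.

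So a stay with TRALI on admission and a later transfusion is counted.

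**Can such stays occur in these data?** Section III.C states "More than 90% of blood transfusions in the United States are performed in inpatient settings", which leaves up to about 10% elsewhere. Appendix A, Table 7, says that the inpatient encounter type "Includes all inpatient stays, same-day hospital discharges, hospital transfers", so patients already ill on arrival are in the cohort.

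**Size.** The protocol states no figure to reproduce. Let p be the share of 518.7 stays that are pre-admission events and r the fraction of those transfused again in the stay. Per 518.7 stay, the true in-stay share is 1 − p and the counted share is (1 − p) + p·r, so

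overstatement = p·r / (1 − p).

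Take p = 0.10 as an upper value. This assumes similar TRALI risk per transfusion in and out of hospital, and admission of all such cases. It does not allow for transfers in.

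- r = 1/3: 0.0333 / 0.90 = 3.7%
- r = 1: 0.10 / 0.90 = 11.1%

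**Against sampling error (illustration).** Section III.B gives about 2 million inpatient encounters a year, and September 2013 through September 2015 is 25 months: 2,000,000 × 25/12 = 4.17 million. Assume that 10% are transfused: 416,667 stays. At the rate of 22.5 per 100,000 cited in III.D, this gives 93.75, or about 94 cases, with an exact Poisson 95% interval of 18.2 to 27.6 per 100,000.

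If a share f of the counted cases preceded the first recorded transfusion, the corrected rate is 22.5 × (1 − f):

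| f | Corrected rate per 100,000 | Overstatement, 1/(1 − f) − 1 |
|---|---|---|
| 5% | 21.4 | 5% |
| 10% | 20.3 | 11% |
| 20% | 18.0 | 25% |

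The interval's half-width is (27.6 − 18.2)/2 = 4.7. At f = 10% the shift is about 2.3, roughly half of that. At f = 20% it is 4.5, about equal to it, but 20% is twice the upper value of p used above.

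**The case against.** The strongest reply is that broad capture is deliberate. Section IV.D calls TRALI likely under-diagnosed and the coded stays potential cases. Section IV.F.5 expects fewer than 200 cases and mainly descriptive results. All Criterion A charts are to be reviewed, with care setting and the closest preceding transfusion recorded, so misordered cases should be found and will lower the PPV reported beside the rate. This stands as a defence of the case finding. It does not repair the rate, because a reader would have to combine the rate and the PPV without guidance. The PPV also mixes wrong order with every other reason for non-confirmation.

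A second reply is that the sequence could be programmed in an analysis plan that is not shown. That is possible, but the protocol itself fixes the numerator codes, the position rule and the data source, and as fixed they contain no order.

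Four stronger readings are tempting, and the documents do not support them.

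- A reader might infer that any respiratory failure causing admission is counted as TRALI. Criteria B and C also need a transfusion-reaction code, and neither is the primary rate.
- A reader might treat a low PPV for Criterion B as a defect. Measuring the algorithm's performance is the third primary objective.
- A reader might infer that a principal-position 518.7 cannot be due to a transfusion in the stay and should be dropped. Table 7 counts emergency visits that become admissions as inpatient encounters, so a causal emergency-department transfusion can lie in the same encounter. The protocol also says nothing about how HCA assigns the principal position.
- A reader might infer that the published rate will be too high overall. Under-diagnosis pulls the other way, so only this one component of bias has a known direction.

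**Conclusion.** The point holds for the primary Criterion A rate: as written, it is a rate of stays with both a TRALI code and a transfusion, and it is labelled as TRALI after transfusion. Under the assumptions shown, the overstatement from this source is about 4% to 11%. Only the figure of more than 90% inpatient transfusions comes from the protocol. Risk per transfusion, admission and retransfusion are assumed, and the true share cannot be derived from the documents. In the illustration, bias of this size stays within the sampling interval, but a larger cohort would not reduce it. Possible misassignment to components is a separate effect that these figures do not measure. Criteria B and C are affected less directly. The point is worth correcting because the charts that would settle it are already to be reviewed.

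**What to change.** Keep any-position capture in Table 5 for case finding and chart selection. In IV.F.2, report the Criterion A rate three ways:

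1. Overall, as now planned.
2. Without stays whose 518.7 is the principal diagnosis or is flagged present on admission, if HCA holds that flag (the protocol does not say). Show these stays on a separate line.
3. Without stays whose charts show onset before the first transfusion in the encounter, counting emergency-department transfusions in that encounter as in-stay.

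In IV.F.3, report the PPV by code position.

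The cost is one program condition, a few table rows and one item on the abstraction form. No extra charts are needed as long as Criterion A stays fit within the 200-chart cap. The drawback is that a position-only exclusion drops some true in-stay cases and misses secondary diagnoses that were present on admission. The second rate is therefore a companion to the first and not a replacement. The third addresses the order of events directly.

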## 3. Quantification of Algorithm Positive Predictive Value

### a. Outcome

We will examine the positive predictive value of electronic TRALI criteria and diagnosis codes through chart review. Medical chart review will be conducted to validate transfusion exposure details for all TRALI cases determined to be definitive, possible, or delayed TRALI cases without regard to whether a prior transfusion record existed in the electronic claims data.

Charts will be adjudicated according to the workgroup approved TRALI clinical case definitions. We will quantify the positive predictive value for each electronic TRALI criterion, as compared to chart review. We will consider stratifying results by age and gender, and also including analysis for possible TRALI and delayed TRALI. Information about indications for blood transfusion, history of prior events will also be collected for analysis in exploratory objectives.

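### Criteria A, B and C in Table 5 can overlap, so the planned PPVs and rates by criterion do not show what B or C each adds to code 518.7

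*Protocol*

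**What the plan says.** Protocol IV.D gives the reason for looking beyond one code: "As TRALI is likely under-diagnosed, this protocol focuses not only on the TRALI specific ICD-9-CM code". Table 5 then defines the electronic criteria:

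- A: code 518.7 in any position.
- B: "Acute respiratory failure ICD-9-CM code in any position (518.81), WITH code for a blood transfusion reaction".
- C: "Other pulmonary insufficiency (518.82), WITH code for a blood transfusion reaction".
- Any: "Criteria A, and/or B, and/or C listed above".

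Neither B nor C carries an exclusion for 518.7. On rates, the text under Table 5 says: "Stratifications will be made by TRALI criterion as feasible". IV.F.2 makes the rate under criterion A primary. On validation, IV.F.3.a says: "We will quantify the positive predictive value for each electronic TRALI criterion, as compared to chart review". IV.E plans the same against definitive TRALI, and then against possible and delayed TRALI. IV.E also sets the chart selection: every A chart, then randomly chosen B or C charts up to a total of 200. None of these sections defines a group of B stays without A, or of C stays without A.

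**The concern.** Criteria that can share stays are not strata. A stay coded 518.7 that also has 518.81 or 518.82 and a transfusion-reaction code is counted in A and again in B or C. Its chart result then feeds the PPV of both.

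B and C were brought in to find TRALI that 518.7 misses, so the informative quantity is the yield among stays that 518.7 does not already capture. The PPV of B as defined mixes that yield with the result in stays that A would have found anyway. If the shared stays have the higher PPV, B looks like a better extension of 518.7 than it is; if they have the lower PPV, it looks worse. Algorithm performance is a primary objective (objective 3 in II.A), so the validation table should not be open to this misreading.

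**Working it through.** **1. The protocol's own figure.** The only figure close to this point is the expectation in IV.F.5 of fewer than 200 cases. It bears on whether every chart would be reviewed. It cannot be reproduced, because the share of inpatient stays with a transfusion is not given. A plausibility check uses about 2 million inpatient encounters a year (III.B), 25 months (IV.A) and 22.5 per 100,000 transfused stays in elderly Medicare beneficiaries (III.D):

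2,000,000 × 25/12 × share × 22.5/100,000 = 937.5 × share.

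Assumed shares of 5%, 10%, 15% and 20% give 47, 94, 141 and 188 cases. The count passes 200 above a share of 200/937.5 = 21.3%. Full review is therefore plausible, and the steps below assume it.

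**2. What B's PPV contains.** Let w be the share of B stays that also meet A. Then

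PPV(B) = w × PPV(A and B) + (1 − w) × PPV(B without A).

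The gap between PPV(B) and the yield of what B adds is w × [PPV(A and B) − PPV(B without A)]. It is zero if w = 0 or if the two PPVs are equal. For illustration, assume 60% in the shared stays and 10% in B without A:

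| A-and-B charts | B-without-A charts | w | PPV(B) |
|---|---|---|---|
| 10 | 40 | 20% | (6 + 4)/50 = 20% |
| 20 | 30 | 40% | (12 + 3)/50 = 30% |
| 30 | 30 | 50% | (18 + 3)/60 = 35% |

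These are 2, 3 and 3.5 times the assumed 10%.

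**3. The same without fixing the two PPVs.** Assume A has 100 stays with 60 true, and B has 60 stays with 30 true. Let t be the number true in B without A. The overlap then holds 30 − t true stays. That number must lie between 0 and the overlap size, and must fit within A's 60 true and 40 false stays. The values of PPV(B without A) that fit are:

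| Overlap | B without A | Possible t | Possible PPV |
|---|---|---|---|
| 0 | 60 | 30 | 50% |
| 10 | 50 | 20 to 30 | 40% to 60% |
| 20 | 40 | 10 to 30 | 25% to 75% |
| 30 | 30 | 0 to 30 | 0% to 100% |
| 40 | 20 | 0 to 20 | 0% to 100% |
| 50 | 10 | 0 to 10 | 0% to 100% |

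At an overlap of 40, 2/20 and 18/20 true among the added stays give the same PPV(A) = 60% and PPV(B) = 50%. Knowing the overlap size does not settle it.

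**4. What Any adds.** Any is a union and counts each stay once, so

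PPV(B or C, without A) = (true in Any − true in A) / (stays in Any − stays in A).

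In the example above, with no stays added by C, Any is 62/120 (51.7%) or 78/120 (65.0%). Subtracting A's 60/100 returns 2/20 or 18/20. With full review, A and Any together identify the combined increment exactly.

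**5. B against C.** Suppose 35 stays meet B or C without A: 15 B only, 15 C only and 5 both. Suppose 14 are true, so the combined yield is 14/35 = 40%. The 14 could all be B-only stays (B without A 14/20, C without A or B 0/15) or all C-only stays (0/20 and 14/15). The totals for B and C need not tell these apart. If the A-and-B overlap holds x true stays in the first case and x + 14 in the second, B has x + 14 true in both. If the A-and-C overlap holds y + 14 and then y, C has y + 14 true in both. A's total is unchanged, as one overlap gains the 14 that the other loses, and so is Any's. This needs two separate overlaps of at least 14 stays each.

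**6. Rates.** With A = 100, B = 60 and an overlap of 40, the two criteria sum to 160 but cover only 120 stays. The rate for A and the rate for Any each count a stay once. Only the rates for B and C repeat stays already counted under A or under each other.

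**The case against.** The strongest reply is that Any is a row of Table 5 beside A. If it counts as one of the electronic criteria, it gets a PPV, and step 4 then gives the combined yield beyond 518.7. IV.F.5 expects few enough cases for full review. This stands, and it rules out a reading that a reader might infer: that even with every chart reviewed the plan cannot show whether going beyond 518.7 brings in true or false cases. What remains is that neither IV.E nor IV.F.3.a clearly says that Any receives a PPV, and that subtraction does not divide the yield between B and C.

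Other replies also have force:

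- The documents say nothing about co-coding. That 518.7 stays often also carry a B or C code pair, or that the stays added by B are mostly false positives, would be inference without support.
- A reader might infer that the headline incidence is double-counted. It is not: the primary rate uses A alone.
- The PPV of B as defined is a valid answer to objective 3, and the protocol states no rule for choosing between A and Any. A demand that some recommendation rest on the stays without 518.7 would go beyond the plan.
- Chart selection takes A first, and each chart's criteria are known, so disjoint groups can be tabulated from the planned data. Table layout is often left to a SAP, which is not shown. But the protocol itself sets reporting by criterion in IV.D, IV.E and IV.F.3.a, and as set this does not deliver the yield of B and of C beyond 518.7.

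**Conclusion.** The point holds in a limited form. B and C overlap with A by definition, so the PPVs and rates for A, B and C do not show what B or C each contributes beyond 518.7, although that is why IV.D includes them. The primary rate and the Any rate are unaffected. The combined contribution can be recovered under full review, provided that Any is reported with counts and a PPV.

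The size cannot be fixed from the documents. It is nil with no overlap or equal PPVs. Under the assumed 60% and 10%, B's PPV exceeds the yield of what it adds by 10 to 25 percentage points at overlaps of 20% to 50%. This is a worthwhile and inexpensive improvement to the validation results; it does not invalidate the design.

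**What to change.** In IV.E, IV.F.2 and IV.F.3.a, report counts, PPVs and rates for three disjoint groups: A; B without A; and C without A or B. Keep the planned results for A, B, C and Any beside them, and state that Any receives a PPV.

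This needs no new charts or data, only further table rows. The cost is small cells and wide confidence intervals for the groups without A, since fewer than 200 cases are expected in all. Showing the counts beside each PPV makes that plain, and IV.F.5 already describes the analyses as likely to be descriptive.
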